5.5. Withdrawal criteria

Enrolled subjects may withdraw from the study:

1. In the case of any serious adverse event.
2. If they decide to do so, at any time, and irrespective of the reason. Reasons provided by the subjects will be documented.
3. If study site participation is discontinued, when the investigator judges it necessary for medical, safety, regulatory or other reasons consistent with applicable laws, regulations and good clinical practice.

6. STUDY DESIGN

6.1. Study method

The experimental design used in this study is a randomised, controlled, within-subject cross-over design. Each individual will undergo a 2-week intervention each of moderate beer consumption and moderate probiotic beer consumption, with a 1-week period of washout in between. The total study duration will be 5 weeks. According to the Health Promotion Board (HPB), the recommendation for safe alcohol consumption is two standard drinks a day for men. For beer, one standard drink is defined as one can of beer at 330ml. The beer used in this study is prepared at 330ml in one can (3.5-5% alcohol) in compliance with one standard beer drink. Only males will be recruited in this study, and they are to consume only one can of normal beer or probiotic beer per day during the study periods, which is within the safe moderate alcohol consumption standards set by HPB.

6.2. Randomisation

Randomization will be done using the research randomizer tool at <http://randomizer.org>. 30 sets will be generated, with each set being randomly assigned a sequence of either (1),(2) or (2),(1). (1) represents the study arm with probiotic beer, while (2) represents the study arm with normal beer.

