5. STUDY POPULATION

5.1. Sample size

The sample size for the present study was calculated with 90% power and a two-sided 0.05 significance level. At least 21 subjects would be needed for this study to find a significant increase in cytokine levels. Based on the 2007 study by Romeo et al. titled 'Changes in the Immune System after Moderate Beer Consumption', there was a significant increase in the cytokine IFNg in men comparing between a 30-day abstinence period and a 30-day moderate beer consumption period. From their data, the standard deviation of the difference between the two periods and the difference in their means was derived as 8287 pg/ml and 6208 pg/ml respectively. Using these values and a 90% power with 0.05 significance level, the minimum sample size was calculated to be 21. To account for a loss to follow-up, 30 subjects will be recruited for this study.

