5.4. Exclusion criteria

1. Female.
2. A current smoker, have smoked, or is a user of tobacco products for the past 2 years.
3. History or presence of current lipid and cardiovascular disorders, respiratory, hepatic, renal, gastrointestinal, endocrine, lipid disorder, haematological, malignancy or neurological disorders capable of significantly altering the performance of the biomarker panel; or of interfering with the interpretation of data.
4. History of alcoholism, alcohol dependence, alcohol abuse, alcohol allergy and/or any other alcohol use disorders.
5. History of Type 1/ Type 2 diabetes and use of anti-diabetic medications in the past.
6. Regular use of medication that are known to have an effect on immune function.
7. Regular use of aspirin.
8. A naïve alcohol drinker.
9. Persons with known or ongoing psychiatric disorders or drug abuse within 3 years.
10. Active infection requiring systemic antiviral or antimicrobial therapy that will not be completed prior to first visit of the study.
11. Treatment with any investigational drug, or biological agent within one (1) month of screening or plans to enter into an investigational drug/ biological agent study during the duration of this study.
12. Significant change in weight (+/- 5%) during the past month.
13. Antibiotic use in the past 2 months.

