6.3. Run-in period

Before each study visit, participants will be informed by the research personnel on the following study requirements:

1. Fast for 10-12 hours prior to reporting for the study visit.
2. Avoid foods high in fat (e.g. fried food) for 24 hours prior to reporting for the study visit.
3. Avoid caffeinated beverages 4-6 hours before reporting for the study visit.
4. Avoid strenuous exercises 24 hours prior to reporting for the study visit.

Subjects are also required to abstain from alcohol and probiotic-containing foods, drinks, or supplements for one week prior to the commencement of the study and during the course of

the study itself. No other alcohol and probiotic-containing foods should be consumed apart from the beer or probiotic beer provided during this duration.

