7. STATISTICAL METHODS

We will utilise data from blood draws to find the change in C-reactive protein, white blood cell count, and cytokine panels from baseline after each study arm to derive summary statistics for each patient.

Data will be analysed using statistical software (eg. SPSS/Stata), with significance defined as *p*-value of less than 0.05 on a two-sided paired t-test. Other variables will be presented as

mean \pm SE. Differences between groups will be analysed using a mixed effect model which can also manage missing data and the presence of unforeseen carryover effects.

For any secondary measurements, paired-t test will also be used to assess baseline versus post-intervention outcomes, compared between the 2 intervention arms.

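### Sequences are randomised without balancing and the planned paired t-test has no period term, so an unequal split passes part of any period difference in the 14-day change into the beer comparison

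*Combined protocol and SAP*

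**What the plan says.** Section 6.2 gives the whole allocation method: "30 sets will be generated, with each set being randomly assigned a sequence of either (1),(2) or (2),(1", where "1) represents the study arm with probiotic beer, while (2) represents the study arm with normal beer". It mentions no block size, fixed total per order, stratification or allocation ratio, and no other section adds one.

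Section 7 takes the change in C-reactive protein, white cell count and cytokines from baseline after each arm, and defines significance as a p-value of "less than 0.05 on a two-sided paired t-test". It also plans a mixed model for differences between groups. That sentence names missing data and carryover, but no period or sequence term.

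Section 6.4 schedules a pre-intervention sample at the start of each period (Visits 2 and 4) and a post-intervention sample at its end (Visits 3 and 5). Section 6.3 requires men to "abstain from alcohol and probiotic-containing foods, drinks, or supplements for one week prior to the commencement of the study" and during it, apart from the study beer. Section 5.4 excludes "A naïve alcohol drinker".

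On numbers, Section 5.1 requires 21 men and adds: "To account for a loss to follow-up, 30 subjects will be recruited for this study".

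**The concern.** In a two-period crossover, an unadjusted paired comparison removes a period effect only when the two orders are equally filled. Independent assignment of 30 men does not secure that, and the test that defines significance has no term to remove what is left. Part of whatever differs between the first and second fortnight would then be reported as an effect of the probiotic.

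A period difference is conceivable here. Visit 2 follows a week off each man's own habitual alcohol and probiotics, whereas Visit 4 follows a week off a standard 14 days of one can a day. Visits 3 and 5 both follow 14 days of one can a day. If starting states differ while end states are alike, the change score itself differs by period. The documents do not show that this happens or how large it would be.

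What is at stake is the estimate from the one split this trial draws, plus a modest loss of precision.

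**Working it through.** **Inputs.** From Section 5.1: "The sample size for the present study was calculated with 90% power and a two-sided 0.05 significance level"; the SD of the paired difference and the mean difference were "derived as 8287 pg/ml and 6208 pg/ml respectively"; 21 men needed, 30 recruited. From Section 6.2: two sequences, assigned set by set. Assumed: probability 0.5 per sequence, independent between men. Also assumed, because the documents give no value: a period difference π in the 14-day change of 0.25 to 0.75 SD of the paired difference (about 2,070 to 6,220 pg/ml).

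**The plan's own figure.** Standardised effect 6208/8287 = 0.749. For a two-sided paired t-test (noncentral t), power is 88.8% at n = 20 and 90.4% at n = 21. The stated 21 reproduces.

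**Distribution of the split.** Binomial(30, 0.5). The share is |n1−n2|/30.

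| Split | Probability of this or worse | Share of π that leaks |
|---|---|---|
| 16:14 | 85.6% | 2/30 = 6.7% |
| 17:13 | 58.5% | 4/30 = 13.3% |
| 18:12 | 36.2% | 6/30 = 20.0% |
| 19:11 | 20.0% | 8/30 = 26.7% |
| 20:10 | 9.9% | 10/30 = 33.3% |

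Exact 15:15 has probability 14.4%. The split is 18:12 or closer in 100% − 20.0% = 80% of randomisations.

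**Why it leaks.** Let τ be the beer effect on the change score and π the period-2 minus period-1 difference in that score. The within-man difference, probiotic minus normal, has mean τ − π in order (1),(2) and τ + π in order (2),(1). The paired mean therefore estimates τ + π(n21 − n12)/N, where n12 and n21 are the numbers of men in the two orders.

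**Size at π = 0.5 SD.**
- 18:12: 0.5 × 8287 × 0.200 ≈ 829 pg/ml, or 829/6208 = 13% of the design difference.
- 20:10: 0.5 × 8287 × 0.333 ≈ 1,381 pg/ml, or 22%.

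**Type I error of the paired t-test given the split.** Simulation with N = 30, unit SD within sequence and 400,000 trials per cell.

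| π (SD) | 15:15 | 18:12 | 20:10 |
|---|---|---|---|
| 0.25 | 4.4% | 5.2% | 6.5% |
| 0.50 | 2.9% | 5.3% | 10.2% |
| 0.75 | 1.5% | 5.1% | 14.0% |

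Averaged over random splits (200,000 trials per shift), the error is 4.9% to 5.1% for all three shifts. With a period term it is 4.8% to 5.2% at every split and shift tried. At 15:15 the unadjusted test falls below 5% because the period difference, though it cancels in the mean, stays in the error variance.

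**Precision with a period term.** Variance relative to a balanced split is N²/(4·n1·n2):
- 18:12: 900/864 = 1.04.
- 20:10: 900/800 = 1.125.

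Power uses noncentrality 0.749 / [0.5·√(1/n1 + 1/n2)] with N − 2 degrees of freedom:
- N = 30: 97.7% at 15:15, 97.3% at 18:12, 96.2% at 20:10.
- N = 21: 90.2% at 11:10, 86.6% at 14:7.

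**The case against.** Simple randomisation is valid and unpredictable. Unconditional type I error is about 5%, and at 18:12 the conditional error is also about 5%. The higher rates need a split that occurs in about 10% of randomisations together with a period difference nobody has measured. All of this stands, and it limits the point to a moderate one.

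Each period has its own pre-intervention sample, so a difference in level alone is subtracted. This also stands. A reader might infer that differing habits before Visit 2 bias the result by themselves. The documents do not support that: only a period difference in the 14-day change can leak. The week of abstinence before Visit 2 also matches the one-week washout before Visit 4, which may shrink any such difference.

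Section 7 plans a mixed model, and a period term would remove the bias at any split. That is correct, but no such term is stated, and significance is tied to the paired t-test.

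Finally, blocking alone would not be enough. Losses from 30 towards 21 can unbalance the orders again, and an unadjusted test at 15:15 is conservative when a period difference exists. This is a good argument for amending Section 7 as well; it does not justify leaving Section 6.2 as it is.

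**Conclusion.** The point holds as a conditional bias that is cheap to prevent. Under independent 50:50 assignment, 86% of randomisations give unequal orders and 36% give 18:12 or worse. Given the split, one fifth (18:12) to one third (20:10) of any period difference in the 14-day change enters the unadjusted beer estimate. The conditional type I error is about 5% at 18:12 and about 6.5% to 14% at 20:10.

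This rests on three things: reading the silence on balancing as simple randomisation, a paired t-test without a period term, and an assumed period difference of 0.25 to 0.75 SD.

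Two stronger readings should be resisted. The plan does not inflate alpha in general, because the error averages about 5% over randomisations. Nor is the sample size wrong: 21 reproduces, and with all 30 men period-adjusted power is still 96% at 20:10. The precision loss matters mainly if completers fall to about 21 and are unbalanced. The change should be made, but its absence does not invalidate the trial.

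**What to change.** In Section 6.2, specify a list with 15 men per order in randomly permuted blocks. Block sizes should vary and be concealed, the list should be prepared before enrolment by someone who does not recruit, and the next order should be hidden from those who do.

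In Section 7, make the primary comparison the mixed model on change from each period's own baseline, with fixed effects for treatment, period and sequence and a random effect for subject, in place of the unadjusted paired t-test. Both changes are needed: the list gives balance at entry, and the period term protects the estimate when dropout disturbs that balance.

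The cost is a few sentences and a different setting when the list is generated. Block sizes must be kept concealed, and the treatment comparison has N − 2 instead of N − 1 degrees of freedom. The list can be changed only before it is in use; the model can be specified at any time before the data are analysed.

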6.3. Run-in period

Before each study visit, participants will be informed by the research personnel on the following study requirements:

1. Fast for 10-12 hours prior to reporting for the study visit.
2. Avoid foods high in fat (e.g. fried food) for 24 hours prior to reporting for the study visit.
3. Avoid caffeinated beverages 4-6 hours before reporting for the study visit.
4. Avoid strenuous exercises 24 hours prior to reporting for the study visit.

Subjects are also required to abstain from alcohol and probiotic-containing foods, drinks, or supplements for one week prior to the commencement of the study and during the course of

the study itself. No other alcohol and probiotic-containing foods should be consumed apart from the beer or probiotic beer provided during this duration.

6.4. Study visits

- Visit 1: Screening**

Individuals will be scheduled to attend a screening session. Research personnel will guide the individual through the inclusion and exclusion criteria to validate their eligibility for the study. Upon confirming that the subject is an eligible study subject, research personnel will explain the study in detail to them in the presence of a witness, and they will be given time to read the approved copy of the informed consent form and the opportunity to ask any questions. Following which, a written informed consent from the individual will be obtained and they will keep a copy of the form.

Anthropometric measurements will be collected, including: height, weight, waist and hip circumference, blood pressure, and body composition measurement using a body composition analyser. A total of 22mL of blood will also be drawn during this visit to test for baseline biomarkers, such as renal and liver function, lipid profile, HbA1c, and blood glucose levels. Plasma will also be obtained and stored to be analysed for further genotyping/biochemical markers. Stool samples will also be collected via a spatula and collection kit for gut microbiota profiling using stool sample collection kits (OMR-200, DNA Genotek, Ontario, Canada) that will be issued during this visit. Subjects are to bring back the stool samples on their next visit. The research personnel will then proceed to schedule the next study visit for the subject.

Subjects are also required to start abstaining from alcohol and probiotic-containing foods, drinks, or supplements for one week prior to the commencement of the study (i.e. Visit 2) and during the course of the study itself. No other alcohol and probiotic-containing foods should be consumed apart from the beer or probiotic beer provided during this duration.

- Visit 2: Pre-intervention blood collection (first arm)**

This visit marks the start of the first study arm. A total of 34mL of blood will be drawn during this visit from the enrolled subjects to test for baseline measurements and for biomarkers including C-reactive protein, white blood cell count, and cytokine panels. Plasma will be also obtained and stored to be analysed for further genotyping/biochemical markers. Stool samples will also be collected from the stool collection kit issued during the screening visit. Another stool collection kit will also be issued for the subjects to bring back their stool samples on their next visit. Next, subjects will be supplied with either normal beer or probiotic beer cans (3.5-5% alcohol, 330ml each), to be consumed only when they have no other dexterity tasks to perform (after working hours, after driving, etc) at the end of the day for the next 14 days. Subjects are to consume only one beer can per day.

- Visit 3: Post-intervention blood collection (first arm)**

This visit marks the end of the first study arm. A total of 34mL of blood will be drawn during this visit from the subjects to test for baseline measurements and for biomarkers including C-reactive protein, white blood cell count, and cytokine panels again after 14 days of intervention.

Plasma will also be obtained and stored to be analysed for further genotyping/biochemical markers. Stool samples will also be collected from the stool collection kit issued during the previous visit. Another stool collection kit will also be issued for the subjects to bring back their stool samples on their next visit. Subjects will then undergo a 1-week washout period before they enter the next arm.

- **Visit 4: Pre-intervention blood collection (second arm)**

This visit marks the start of the next study arm. A total of 34mL of blood will be drawn during this visit from the subjects to test for baseline measurements and for biomarkers including C-reactive protein, white blood cell count, and cytokine panels. Plasma will be also obtained and stored to be analysed for further genotyping/biochemical markers. Stool samples will also be collected from the stool collection kit issued during the previous visit. A final stool collection kit will also be issued for the subjects to bring back their stool samples on their next visit. Subjects will then be supplied with either normal beer or probiotic beer cans (3.5-5% alcohol, 330ml each), depending on which arm they started with first, to be consumed only when they have no other dexterity tasks to perform (after working hours, after driving, etc) at the end of the day for the next 14 days. Subjects are to consume only one beer can per day.

- **Visit 5: Post-intervention blood collection (second arm)**

This visit marks the end of the second study arm. A total of 34mL of blood will be drawn during this visit from the subjects to test for baseline measurements and for biomarkers including C-reactive protein, white blood cell count, and cytokine panels. Plasma will be also obtained and stored to be analysed for further genotyping/biochemical markers. Stool samples will also be collected from the stool collection kit issued during the previous visit.

There will be blood collection during all visits. In total, approximately 158mL (=10 to 11 tablespoons) of blood will be collected for this study. For comparison, about 450 mL (=30 tablespoons) of blood is the amount taken when a person donates blood. Any leftover blood samples will be stored in a -80°C freezer for no longer than 5 years after study completion and will be used for future general research only if subjects have given informed consent.

6.5. Incidental Finding Management Plan

6.5.1. Description of the Incidental Findings (IF) that may be returned

IFs that may be returned are blood test results that are outside the expected normal range. Blood test results in this study includes liver panel, renal panel, lipid panel, insulin, glucose (fasting), HbA1c, C-reactive protein, and full blood count.

6.5.2. Plans to verify the presence of a suspected IF

In the informed consent form, participants will be asked their wish to re-identify and be notified in the case of an incidental finding. The study team will keep a record of answer (Yes or No) in a study log to keep track. Blood test results will be reviewed by a research assistant and

any test results not within range will be noted and communicated to the PI to determine if the result is clinically significant and actionable.

6.5.3. The mode of communication to be used and the limits of effort of re-contacting

The mode of communication used to notify the participant will be face-to-face or via phone call. The participant will be notified face-to-face by the last visit, if the IF was found before the participant's last visit.

If the IF was found after the last visit, the findings will be communicated via phone call. The limits for this effort of re-contacting will be that the participant cannot be reached via phone. In such cases, the research team will attempt to call the participant again at two separate timings. If the participant still cannot be reached, the research team will contact the participant's next-of-kin, whose contact information is stated in the informed consent form by the participant.

6.5.4. Plans for counseling or referrals for the research participant, if applicable

In the event that the findings are determined to be clinically significant and actionable, and if the participant agrees to be re-identified and notified, a study doctor will explain the incidental finding (IF) and will refer the research participant to go for standard-of-care testing and interpretation of results by a qualified professional at an accredited clinical facility.

6.5.5. Any other relevant considerations (e.g. incidental finding has public health implications, participants are less than 21 years old, participants' preference to be re-identified is unknown or subjects are uncontactable etc.)

In the event of the discovery of an IF with public health implications, the research team will notify participants of the IF, regardless of their initial indication in the informed consent form. As only participants aged 21 and above will be recruited for this study, the participant themselves will personally indicate their preference in the consent form. During informed consent, the study coordinator administering the consent will review the consent form and check that the participant has ticked their preference to be re-identified and notified of an IF (Yes or No) in the consent form. This is to ensure that the participant's preference to be re-identified or not is known to the research team. If they agree to be re-identified and notified of an IF (i.e. ticked 'Yes'), they will also need to fill in the contact details of the next-of-kin, as reflected in the form.

7. STATISTICAL METHODS

We will utilise data from blood draws to find the change in C-reactive protein, white blood cell count, and cytokine panels from baseline after each study arm to derive summary statistics for each patient.

Data will be analysed using statistical software (eg. SPSS/Stata), with significance defined as *p*-value of less than 0.05 on a two-sided paired t-test. Other variables will be presented as

mean \pm SE. Differences between groups will be analysed using a mixed effect model which can also manage missing data and the presence of unforeseen carryover effects.

For any secondary measurements, paired-t test will also be used to assess baseline versus post-intervention outcomes, compared between the 2 intervention arms.

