2.4. Rationale for Study Design

A within-subject crossover study design is utilised to compare the immunological outcomes of moderate beer drinking and moderate probiotic beer consumption.

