3. HYPOTHESIS AND OBJECTIVE

3.1. Hypothesis

The moderate consumption of probiotic beer is hypothesised to improve gut health and immunological parameters.

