3.2. Objective

The objective of this research is to study the immunological and gut microbiome effects of moderate probiotic beer consumption.

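### Several immune markers are tested at two-sided 0.05 with no primary endpoint, no stated adjustment and no rule for how they jointly support the hypothesis

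*Combined protocol and SAP*

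**What the plan says.** Section 7 is the only statistical section.

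- **Markers.** Blood draws are used "to find the change in C-reactive protein, white blood cell count, and cytokine panels from baseline after each study arm". The members and number of the cytokines are not given.
- **Test.** Significance is a p-value "less than 0.05 on a two-sided paired t-test". The section then adds: "Differences between groups will be analysed using a mixed effect model", a model also expected to deal with missing data and carryover.
- **Secondary measurements.** "For any secondary measurements, paired-t test will also be used". Nothing is named as primary for these to be secondary to, and no microbiome measure appears.
- **Hypothesis and objective.** Section 3.1: "The moderate consumption of probiotic beer is hypothesised to improve gut health and immunological parameters". Section 3.2 aims to "study the immunological and gut microbiome effects of moderate probiotic beer consumption". Neither says which marker, or how many, must improve.
- **Comparison.** Section 2.4 gives the purpose of the crossover as to "compare the immunological outcomes of moderate beer drinking and moderate probiotic beer consumption".
- **Sizing.** Section 5.1: "At least 21 subjects would be needed for this study to find a significant increase in cytokine levels". The figure comes from one cytokine, IFNg, in a published comparison of 30 days of moderate beer with 30 days of abstinence (difference 6208 pg/ml, SD of the difference 8287 pg/ml). Thirty men are to be recruited. Section 7 does not mention IFNg.

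**The concern.** A 5% level applied to each marker separately does not give a 5% level for a conclusion that may rest on whichever marker turns out significant. With no primary, hierarchy or adjustment, such a conclusion would be consistent with the plan as written.

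Direction is also open. Sections 1.1 and 2.3 look for an anti-inflammatory effect, while Section 5.1 expects cytokines to rise, and no marker has a stated favourable sign. This does not raise a two-sided error rate, but it lets a change of either sign be described as benefit.

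The power statement does not fill the gap. It concerns one cytokine and a contrast with abstinence, whereas Section 2.4 compares two beers, each drunk for 14 days.

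**Working it through.** **1. The plan's own sample size.** Inputs from Section 5.1: difference 6208, SD of the difference 8287, two-sided 0.05, power 90%. Standardised difference = 6208/8287 = 0.749. Paired t-test power from the noncentral t distribution is 88.8% at n = 20, 90.4% at n = 21 and 98% at n = 30. The stated minimum of 21 reproduces, for one marker tested once.

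**2. Chance of at least one false positive.** The documents give neither the number of cytokines nor the correlations, so both are assumed. Three markers (CRP, white cells, one cytokine) is the least the text allows; 12 illustrates a larger panel. With independent markers:

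- either direction counts: 1 - 0.95^3 = 14.3%; 1 - 0.95^12 = 46.0%
- only a pre-set favourable direction counts (0.025 per marker): 1 - 0.975^3 = 7.3%; 1 - 0.975^12 = 26.2%

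For correlated markers I simulated paired t-tests on equicorrelated within-person differences with no true effect, 60,000 trials per setting. The favourable-direction column takes markers to be positively correlated in that direction. The last column is a primary tested at 0.05 beside a Holm family of the remaining markers, with no gate between them. Entries are percentages, n = 21 / n = 30.

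| Markers | Correlation | Any marker, either direction | Any marker, favourable direction | Primary plus ungated Holm |
|---|---|---|---|---|
| 3 | 0 | 14.1 / 14.4 | 7.1 / 7.4 | 9.7 / 9.8 |
| 3 | 0.5 | 12.8 / 12.5 | 6.4 / 6.4 | 8.8 / 8.6 |
| 3 | 0.8 | 10.0 / 10.0 | 5.0 / 5.0 | 7.1 / 7.0 |
| 12 | 0 | 45.6 / 45.7 | 25.7 / 25.9 | 9.4 / 9.6 |
| 12 | 0.5 | 33.3 / 32.7 | 16.5 / 16.4 | 8.4 / 7.9 |
| 12 | 0.8 | 19.2 / 19.1 | 9.5 / 9.5 | 5.8 / 5.8 |

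At correlation 0.9 the either-direction figures fall to 8.4% and 13.5%. All figures count one test per marker.

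**3. Effect of a gate.** If the Holm family is opened only when the primary is significant, two cases cover everything. If the primary has no true effect, any false positive requires the primary to be rejected first, which has probability 5%. If it has a true effect, the only possible false positives are in the Holm family, which is held at 5%. The overall error is therefore at most 5%.

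**4. Power for the between-beer contrast.** The documents give no SD for the difference between two changes from baseline. Assume each change has SD 8287, with correlation r between the two changes in the same man. Then SD of contrast = 8287 × sqrt(2(1 - r)).

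- r = 0: SD = 11,720; 6208/11,720 = 0.530; power 64% at n = 21, 80% at n = 30.
- r = 0.5: SD = 8287; power 90% at n = 21, 98% at n = 30.

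These hold for a between-beer difference of 6208 pg/ml. That figure is borrowed from the abstinence comparison; the documents give no expected difference between the two beers.

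**The case against.** The strongest reply is that no section says any one marker in either direction suffices. The hypothesis speaks of improvement, which is directional, and counting only favourable changes roughly halves the figures. That stands, and both sets of figures are shown for this reason. But no favourable sign is fixed for any marker, so the two-sided scenario is not excluded either.

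A second reply is that IFNg is the implied primary because the study was sized on it. Section 5.1 uses it only to derive a number and otherwise speaks of cytokines in general; Section 7 does not name it. If it was meant as primary, one sentence would settle the matter.

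A third is that this is a small study of a new question, for which exploratory labelling would be enough. That is a legitimate choice, but the protocol never calls itself exploratory, and it states both a hypothesis and 90% power.

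On the two methods, a reader might infer that Section 7 gives the paired t-test and the mixed model no roles at all. That goes too far: it ties significance to the first and between-group differences to the second. The roles are loose, and what is missing is a statement of which result decides.

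**Conclusion.** The concern holds in limited form. The plan has no primary endpoint, no stated adjustment and no rule for combining markers, so a claim resting on any one of them would not carry 5% error control. Its size depends on assumptions: about 10-14% (3 markers) to 19-46% (12) if either direction counts, and about 5-7% to 9-26% if only a favourable one does, for common correlation 0.8 to 0.

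Two stronger readings are not supported. A reader might infer that the plan has a false-positive rate of up to 46%; that is one scenario under a decision rule, a panel size and a correlation the documents do not state. A reader might also infer that the study is underpowered or that 21 is miscalculated. The arithmetic is right for its own inputs. For the between-beer contrast, power cannot be derived from the documents: under the assumptions above it runs from 64% to 90% at n = 21 and from 80% to 98% at n = 30.

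This should be corrected before analysis. Confidence is medium, because the panel and the intended decision rule are unknown.

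**What to change.** Before analysis, amend Sections 5.1 and 7 as follows.

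1. Name one marker as the single primary endpoint, defined as the probiotic-minus-normal-beer difference in change from each period's own baseline, with its expected direction and the reason for it. IFNg is the only marker used for sizing.
2. Test it at two-sided 0.05 with the mixed model (beer, period and sequence as fixed effects, subject as random effect), since Section 7 already gives that model the between-group differences. Keep the paired t-test as a sensitivity analysis.
3. State that the hypothesis is judged on this primary only and that no other marker can replace it.
4. List CRP, white cell count and every other cytokine by name. Either test them with Holm only if the primary is significant, which keeps the overall error at or below 5%, or label them exploratory. An ungated Holm family beside a full-5% primary would give about 6-10% overall.
5. Label the microbiome results exploratory, or put one named measure in the secondary family.
6. State that n = 21 and 90% power apply to a 30-day beer-versus-abstinence IFNg difference of 6208 pg/ml with SD 8287, and give the range of power for the 14-day between-beer contrast as an assumption.

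**Cost.** Wording only. Recruitment can stay at 30 with the power statement restated, and the primary keeps its full 5%. The other markers and the gut-health claim face a stricter threshold or a weaker status, and the power statement becomes less favourable.
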